### **Safety Assessment**

Safety will be assessed by recording the nature and incidence of adverse events and serious adverse events. Adverse events will be assessed by direct questioning. An adverse event is defined as any unfavourable, unintended sign, symptom, syndrome or disease that develops or worsens with the use of a medicinal product, regardless of whether it is related to the medicinal product. All adverse events must be recorded on the case report form. A serious adverse event is defined as any untoward medical occurrence that at any dose:

- results in death, is life threatening
- requires hospitalization or prolongation of hospitalization
- results in a persistent or significant disability or incapacity
- Is a congenital anomaly or birth defect.

‘Life-threatening’ means that the person will be at immediate risk for death; it does not refer to an adverse event that might have caused death if it were more severe. ‘Persistent or significant disability or incapacity’ means that a person’s ability to carry out normal life functions is substantially disrupted. All serious adverse events occurring during the study must be recorded and reported by the principal investigator to the sponsor, regardless of whether the principal investigator considers the events to be related to the investigated medicine. The investigator will collect information on all people who become pregnant while participating in this study and will record the information on the appropriate form. The person will also be followed to determine the outcome of the pregnancy.

### **Emergency Care**

Any patient with treatment failure or recrudescence will receive second line drugs. This will be given orally unless the patient has persistent vomiting, in which case it will be given Artesunate IM/IV until the vomiting resolves and then will be switched to oral therapy.

Patients with signs of severe malaria (altered mental status, coma, convulsions, hemoglobin <5g/dl, respiratory distress, circulatory collapse, or abnormal bleeding), persistent vomiting or

severe side effects will be hospitalized and receive parenteral therapy with artesunate and relevant supportive treatments, according to National Guidelines.

We will counsel patients and parents to return immediately if they or their child develops a raised rash (urticaria) or difficulty breathing suggestive of a severe allergic reaction. These patients will be treated with diphenhydramine or chlorpheniramine and will be withdrawn from the study. In addition, patient and or their parents, caretakers and family members will be counseled that the patient should not receive additional doses of the antimalarial they were given. These patients will be treated with oral quinine for seven days as per the rescue protocol.

Adult patients and parents with children in the study will be encouraged to return to the clinic for any fever or other signs of illness on any day during the 42-day follow-up period, allowing for early detection and treatment of illness before it becomes severe. Any hospitalization which occurs during the 42-day follow-up period will be paid by the study team.

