## Sample Size Determination and Sampling Technique

### Sample Size Determination

The sample size will be determined according to the WHO (2009) protocol(11); by using the single population proportion formula and calculated assuming 5% margin of error, 95% confidence interval (CI), and treatment failure of 5% and 20% loss to follow-up rate. Accordingly, a minimum of 73 patients will be enrolled.

$$\text{Sample size (n)} = \frac{[(Z \alpha/2)^2 p(1-p)]}{d^2}$$

$$\frac{(1.96)^2 0.05 (1-0.05)}{(0.05)^2} = 73$$

Assuming an additional 20% loss to follow-up rate and withdrawal of consent (15 patients) during the study, at least 88 (73 + 15) patients will be required to bring about a representative sample size.  $n = (1+0.2) 73 = 88$  Where, n= sample size

P=Expected treatment failure (5%)

Z=confidence interval (95%)

d=margin of error (5%)

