## Rescue Treatment

Patients failing in any arm will be treated with second line drug per National Guidelines. Whereas, patients failing with the second line will be administered as of severe malaria criteria that is an indication of treatment failure.

The following are the known efficacy and adverse effects and pharmacokinetics of treatment drugs that will be used in the study:

**Chloroquine Plus Primaquine (CQ+PQ):** Chloroquine Plus Primaquine is a WHO Pre-qualified anti-malarial and FDA approved; WHO certifies the quality, safety and efficacy of the medication, and verifies that the manufacturer complies with WHO Good Manufacturing Practices. CQ+PQ is currently the first line anti-malarial recommended by Ethiopia FMOH for the treatment of uncomplicated falciparum infection. Adverse events are generally mild, most commonly GI (vomiting and diarrhea) and hematologic (anemia and eosinophilia). Its safety will be demonstrated in studies from Ethiopia and Uganda. Chloroquine has a half-life of 30-60 hours (53,54), while primaquine has a elimination half-life of 5-7 hours (54).

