### Treatment Failure (TF)

Clinical deterioration due to *P. vivax* illness requiring hospitalization in the presence of parasitemia

Presence of parasitemia and axillary temperature  $\geq 37.5^{\circ}\text{C}$  on any day between day 3 and day 28/42

Presence of parasitemia on any day between day 7 and day 28/42, irrespective of clinical condition

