## ANNEX 5: Drug Dosing and Regimens

All patients will be weighed to determine the accurate weight-based dose for all drugs.

- **Chloroquine:** Total of 25mg base per kg over 3 days (10 mg base/kg on Days 1 and 2, and 5 mg base/kg on Day 3). 500 mg tablets. We will use the syrup (10mg/ml) formulation for children < 4 years of age, if available.

Weight (kg)	Age	Day 1	Day 2	Day 3
5–6	<4 mo	¼ tablet (5 ml syrup)	⅛ tablet (5 ml syrup)	⅛ tablet (2.5 ml syrup)
7–10	4–11 mo	¼ tablet (7.5 ml syrup)	¼ tablet (7.5 ml syrup)	¼ tablet (5 ml syrup)
11–14	1–2 yrs	½ tablet (12.5 ml syrup)	½ tablet (12.5 ml syrup)	¼ tablet (7.5 ml syrup)
15–18	3–4 yrs	½ tablet (15 ml syrup)	½ tablet (15 ml syrup)	½ tablet (15 ml syrup)
19–24	5–7 yrs	¾ tablet (20 ml syrup)	¾ tablet (20 ml syrup)	½ tablet (15 ml syrup)
25–35	8–10 yrs	1¼ tablet	1¼ tablet	½ tablet
36–50	11–13 yrs	1½ tablet	1½ tablet	1 tablet
> 50	14+ yrs	2 tablet	2 tablet	1 tablet

--	--	--	--	--

**Primaquine:** 7.5 mg base tablet. Medication given as 0.25mg/kg daily for 14 days in people with normal G6PD levels. In people with G6PD deficiency, 0.75 mg/kg (45 mg) once a week for 8 weeks.

Body Weight (kg)	Single dose of primaquine (mg base)
5 to 10	Weight-based using extemporaneous preparation as outlined by Sanofi
10 to < 25	3.75
25 to <50	7.5
50 to 100	15

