#### **Day 2:**

---

- Clinical assessment — referral in case of severe malaria/danger signs
- Measurement of axillary temperature
- Blood sampling for blood smears and filter paper
- Treatment, third dose or alternative treatment in case of early treatment failure

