#### **Any other day:**

- Clinical assessment — referral in case of severe malaria/danger signs

- Measurement of axillary temperature
- Blood sampling for blood smears and filter paper
- Hemoglobin/hematocrit if indicated clinically
- Alternative treatment in case of treatment failure

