## ANNEX 9: Schedule of Follow-Up Activities

	day 0	day 1	day 2	day 3	day 7	day 14	day 21	day 28	day 35	day 42	any other day
PROCEDURES											
Clinical assessment	X	X	X	X	X	X	X	X	X	X	X
Temperature	X	X	X	X	X	X	X	X	X	X	X
Blood slide for parasites count	X	X	X	X	X	X	X	X	X	X	X
Hemoglobin	X					X		X		X	X
Filter paper	X			X	X	(X)	(X)	(X)	(X)	(X)	X
Drug adverse event monitoring	X	X	X	X	X	X	X	X	X	X	X
TREATMENT											
Drug to be given	X	X	X								(X)
Rescue treatment		(X)	(X)	(X)	(X)	(X)	(X)	(X)	(X)	(X)	(X)

NOTES: Parentheses denote conditional or optional activities. Rescue treatment could be given on any day, provided that the patient meets the criteria for treatment failure. Extra days are any days other than regularly scheduled follow-up days when the patient returns to the facility because of recurrence of symptoms.

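### Emergency Care orders seven days of oral quinine after any suspected severe allergic reaction, without requiring unfinished chloroquine or treatment failure, so a patient with no infection left to treat would also receive it.

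*Combined protocol and SAP*

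**What the plan says.** The Emergency Care section tells patients and parents to return at once for hives or breathing trouble that points to a serious allergy. Such patients receive an antihistamine, leave the study and are advised to take no more of the antimalarial they had been given. The section then says: "These patients will be treated with oral quinine for seven days as per the rescue protocol".

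The parts of the plan that bear on this order are:

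- **Rescue Treatment:** "Patients failing in any arm will be treated with second line drug per National Guidelines". Neither quinine nor a seven-day course is named there.
- **Annex 9, notes to the follow-up schedule:** "Rescue treatment could be given on any day, provided that the patient meets the criteria for treatment failure".
- **Annex 8, Day 2:** "Treatment, third dose or alternative treatment in case of early treatment failure". The third dose completes the three-day chloroquine course.
- **Annex 5, primaquine:** "Medication given as 0.25mg/kg daily for 14 days in people with normal G6PD levels". Patients with G6PD deficiency take a weekly dose for 8 weeks instead.
- **Annex 4, Treatment Failure:** "Presence of parasitemia on any day between day 7 and day 28/42, irrespective of clinical condition". Every other failure criterion in Annex 4 also requires parasitaemia.
- **Annex 8, any other day:** "Blood sampling for blood smears and filter paper".

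**The concern.** The trigger for quinine is the allergic reaction alone. The order does not ask whether blood-stage treatment is unfinished or whether it has failed. On days 0 to 2 this does no harm, because chloroquine has been interrupted and something must replace it. After day 2 the blood-stage course is complete, yet exposure to primaquine continues and a reaction remains possible.

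At stake is the care of a patient who has just had a suspected severe drug reaction. Followed literally, the text gives that patient a further drug for seven days with no infection to treat. The plan itself recognises hypersensitivity to alternative drugs as a risk: a history of it is an exclusion criterion.

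**Working it through.** The main check is a comparison of texts. The arithmetic only sizes the point.

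**1. Is there a condition in the order itself?** No. The nearest limit is the advice to take no more of the drug already given. That suggests a reaction during dosing, but it does not make quinine depend on an unfinished course.

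**2. Does the cross-reference to the rescue protocol supply one?** No. Rescue Treatment and the Annex 9 note both concern patients who fail. Since every Annex 4 criterion needs parasitaemia, an allergic patient without parasites is not a failure, and neither text says what that patient should get.

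**3. Can the case arise?** Yes. Chloroquine is given on days 0, 1 and 2. If primaquine also starts on day 0 (an assumption; the start day is not stated), its 14 days are days 0 to 13. Days 3 to 13 fall after the last chloroquine dose: 13 − 3 + 1 = 11 of 14 days.

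**4. How many such patients would not be treatment failures?** Sample Size Determination plans for 5% failure over the whole follow-up. If that holds, at most 5% have met a failure criterion by any given day, so at least 95% have not, assuming that reactions and failure are unrelated. From day 7 any parasitaemia counts as failure, so from then the 95% also describes patients with a negative smear. On days 3 to 6 it does not, because some parasitaemia then is not failure.

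**5. How many patients?** The documents give no reaction rate. The inputs are:

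- N = 88 (Sample Size Determination)
- r, the share of patients who react: 0.5% to 2% (assumed)
- s, the share of reactions after chloroquine is complete: 20% to 50% (assumed)
- q, the share not failing: 0.95 (step 4)

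Unneeded courses = N × r × s × q.

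- Low: 88 × 0.005 × 0.20 × 0.95 = 0.084
- High: 88 × 0.02 × 0.50 × 0.95 = 0.836

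**6. Sensitivity.** The planning value for failure hardly matters: with q = 1 the range is 88 × 0.005 × 0.20 = 0.088 to 88 × 0.02 × 0.50 = 0.88. Timing matters more. If reactions were spread evenly over the primaquine days, s would be 11/14 = 0.786, and the range would be 88 × 0.005 × 0.786 × 0.95 = 0.33 to 88 × 0.02 × 0.786 × 0.95 = 1.31.

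**The case against.** The strongest reply is that the authors meant quinine to replace an interrupted course. The quinine sentence follows directly on the advice to stop the study drug, and Annex 9 marks routine dosing on days 0 to 2 only, with an optional mark for any other day. That is probably the intent. It is not written as a condition, however, and Annex 5 keeps patients on primaquine well past day 2. General statements elsewhere, that patients will be treated appropriately and that their well-being comes first, do not clearly displace an order naming a drug and a duration.

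A reader might go further and infer that Emergency Care and Annex 9 give opposite instructions for the same patient. The documents do not support that. The Annex 9 note is permissive and belongs to the schedule for patients still in follow-up, whereas allergic patients are withdrawn. The plan also treats other withdrawn patients without any failure criterion: those who vomit twice are referred for parenteral artesunate. What stands is that the cross-reference points to rescue rules which do not cover this case.

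The national guidelines, which are not in the documents, might contain a suitable condition. But the quinine sentence does not refer to them; Rescue Treatment does, and only for failing patients.

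A reader might also extend the point to the sentence that sends severe side effects to hospital with parenteral artesunate. That sentence expressly follows the national guidelines, so a missing smear condition cannot be shown. Carving allergic reactions out of it would also remove hospital admission and supportive care from patients with breathing difficulty.

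Finally, the small numbers rest on assumed rates. That is correct, and it limits the weight of the point, not its accuracy.

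**Conclusion.** The point holds as an over-broad treatment instruction. As written, a patient who has completed chloroquine, has no parasitaemia and then reacts, for example while on primaquine, receives seven days of quinine without an infection to treat. The order is sound for reactions on days 0 to 2.

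Probably fewer than one patient in the trial would be affected. This rests on the assumed reaction rate and on the assumption that no more than half of reactions come after day 2; with evenly spread reactions at the 2% rate the figure would be slightly above one. A reader might infer a bias in the cure rate, but none follows: these patients are withdrawn whether or not they get quinine. The case for changing the text is patient care at very little cost.

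**What to change.** In Emergency Care, keep the antihistamine, the stop of study drug and the withdrawal. Replace the quinine sentence with:

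> Read the blood smear taken at this visit. Give oral quinine for seven days only if the three chloroquine doses are not complete or the patient meets a treatment failure criterion in Annex 4. Otherwise give no further blood-stage treatment, repeat the smear if fever returns, and manage any unfinished primaquine per National Guidelines.

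The condition should be a failure criterion and not simply a positive smear. Low parasitaemia without fever on day 3, below 25% of the day 0 count, is not failure under Annex 4, and such a patient may be clearing normally after full chloroquine.

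Optionally, add to the Annex 9 note that replacement treatment after an allergic withdrawal follows this rule. Leave the sentence on hospital admission and supportive care for severe side effects as it is.

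The cost is one conditional passage and, if wanted, one clause in Annex 9. No extra sample is needed, because Annex 8 already takes a smear at any unscheduled visit. The small downside is that the smear must be read before the treatment decision; the rapid Giemsa stain in Laboratory Examination takes 10 to 15 minutes. The antihistamine need not wait for it.

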### **Response to unexpected incidents**

If sufficient numbers of malaria cases are presenting to the clinic but enrolment is insufficient, the supervisor will need to determine the problem and take needed actions to rectify the problem. In case of low patient recruitment due to unusually low transmission of malaria, necessary steps will be taken to either rectify the problem or to find a new site.

## **Screening and Enrollment Procedures**

### **Screening**

Screening for eligible patients at the study sites will be done in the following fashion:

1. All patients over 6 months with temperature  $\geq 37.5^{\circ}\text{C}$  or a history of fever in the last 48 hours will have screening blood smear performed as per the national diagnosis and treatment guidelines at the health centers. Patients with microscopy confirmed *P. falciparum* or *P. vivax*, age greater than 6 months, and living within 5 km of the health center will be screened.
2. For all facilities, if the patient meets the screening criteria and the patient or the parent or guardian consents to enrollment, they will be assigned a consecutive, unique number that will become the patient's study number and will be used to identify all forms and blood samples from that patient. Enrollment will be conducted by a staff member not involved in

the clinical assessment of the participant to ensure that consent is freely given.

3. A screening form containing demographic, clinical, and laboratory information will be started on each smear positive patient, thus allowing for appropriate tracking of each patient through the screening procedure.
4. The patient's body weight will be measured to the nearest kilogram, using a hanging scale for weighing young children, or a floor scale for large children/ adults and recorded on the demographic form. The circumference of the left upper mid-upper arm will be measured at the mid-point between the elbow and shoulder, and will be recorded to the nearest 0.2 cm. Edema will be assessed by thumb pressure for 3 seconds on the dorsal surface of both feet.

### **Enrollment and Follow-up**

If a patient meets the initial screening criteria and permission to participate in the study is obtained, the patient will go through the enrolling process.

1. The patient will be evaluated by clinical staff for signs of febrile illness other than malaria, (including but not limited to pneumonia, otitis media, tonsillitis, measles, chicken pox, abscesses) and signs of severe disease/danger signs, as presence of any of these will exclude the patient from participating in the study. Patients found to have any of these conditions will be treated appropriately per National Guidelines, and referred to the referral hospital as necessary. A standardized form listing demographic and clinical information will be completed on each patient.
2. Urine pregnancy test will be conducted on all women of reproductive age. Anyone testing positive will be excluded.
3. Those enrolled will have a second finger prick performed to assess for the following:
  - Thin smear will be used to verify parasite species and to conduct a formal parasite count. Rapid test will also be done for better speciation. Two microscopists will independently read each smear; if the 2 readings are >50% discordant, a third expert microscopist will examine the slide and make the final decision.
  - Hemoglobin measurement (Hemocue™ Hb301+; HemoCue, Angelholm, Sweden) will be carried out and those with hemoglobin <5g/dL will be excluded.
  - Filter paper will be obtained for molecular testing and drug levels.
4. Participants testing positive for *P. Vivax* will receive CQ+PQ. A Convenient sampling technique will be used. The study will not be blinded.

5. After assignment, on day 0, each patient will receive the dose of treatment medication under direct observation and will be monitored for vomiting. Each patient will return on days 1 and 2 for subsequent doses. Clinical reassessments will be made on days 1- 3, 7, 14, 21, 28, 35, and 42 (see Annex VI). Participants will be given 100 Ethiopian Birr for each visit to cover their travel expenses (this is a compensation for a round-trip transportation to the clinic). Patients will be advised to return on *any* day during the follow-up period if symptoms return and not to wait for scheduled visit days. Patients who do not present to the facility for follow-up visits will be followed at home. This is standard for *in vivo* studies based on the WHO protocol, but is not the standard for routine care. Typically, for patients not enrolled in a study, the parent would be given all the doses of the medicine to administer at home, and no follow-up would be scheduled. The parent would be told to return if they did not improve.
6. Blood films (thick and thin) for parasite count and dried blood spot will be obtained and examined as described above. All samples will have the study ID number and date of collection, but no other personal identifiers. The logbook that links the study ID number to the patient will be kept at the study site locked in a cabinet when not in use during the study enrollment period. After the completion of the study, this logbook will be stored at EPHI.
7. If patients do not appear for scheduled follow-up, the study team will attempt to reach them at home. After day 3, patients who fail to return on their scheduled day but return one day early or one day late may still be included in the analysis.
8. A case report form will be used to record the general information and clinical observations on each patient enrolled into the study. The appointment schedule will be clearly explained, and a follow-up card with a personal identification number will be provided. The study schedule (Annex VI) and follow-up schedule is summarized in (Annex VII).

**Storage of specimens:** Specimens obtained in this study will be saved for the duration of specified testing. Specimens will not be tested for HIV.

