#### Exclusion Criteria

- ♣ Severe malaria with complication sign and symptoms (see Annex I)
- ♣ Signs or symptoms of severe malnutrition, defined as weight-for-age  $\leq$  3 standard deviations below the mean, symmetrical edema involving at least the feet, or mid-upper arm circumference <100 cm for children less than five years of age (NCHS/WHO normalized reference values; see Annex I)
- ♣ Mixed plasmodium infection
- ♣ Severe anemia, defined as hemoglobin (Hb) < 8 g/dl

- ♣ Presence of febrile conditions caused by diseases other than malaria (e.g. measles, acute lower respiratory tract infection, severe diarrhea with dehydration)
- ♣ Serious or chronic medical condition (e.g. cardiac, renal, hepatic diseases, sickle cell disease, HIV/AIDS)
- ♣ Positive pregnancy test or breastfeeding
- ♣ Unable or unwilling to take contraceptives for women of child-bearing age
- ♣ Children weighing less than 5 kilograms
- ♣ History of hypersensitivity reaction to any medication tested or used as an alternative treatment
- ♣ Participants with history of prolonged QT conditions
- ♣ Taking regular medication, which may interfere with antimalarial pharmacokinetics or efficacy (see Annex VII)?

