#### **Patient Discontinuation or Protocol Violation**

Patients meeting any of the following criteria will be withdrawn:

- Withdrawal of consent
- Failure to complete the treatment
  - Vomiting both initial and replacement doses at any single time in the treatment (i.e. If the patient vomits both attempts to administer the morning dose that would

- require withdrawal; however, vomiting the initial morning dose but not the morning replacement dose would not require withdrawal), persistent vomiting
- Severe side-effects necessitating hospitalization
  - Progression to severe malaria
  - Failure to attend the scheduled visit during the first 3 days
  - Enrolment violation
    - Severe malaria on day 0
    - Erroneous inclusion of a patient outside of the inclusion/exclusion criteria
  - Voluntary protocol violation: Antimalarial (or antibiotics with antimalarial activity) treatment administered by a third party or self-medication with antimalarial (or antibiotics with antimalarial activity) assessed by asking participants or their caretaker at follow-up visits (Annex VI)
  - Involuntary protocol violation
    - Occurrence during the follow-up of concomitant disease that would interfere with a clear classification of the treatment outcome
    - Detection of a mono-infection with another malaria species during follow-up
    - Misclassification of a patient due to a laboratory error (parasitemia) leading to the administration of the rescue treatment

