## ANNEXES

## Annex 1. Patient Screening Form

## Patient Screening Form

STUDY SITE CODE: \_\_\_\_\_

TREATMENT GROUP: \_\_\_\_\_

1. Names:	2. Date: (dd/mm/yy) ____ / ____ / ____	3. Weight (kg):
4. Age*: years _____ months. _____	5. Gender: M _____ F _____	

1.	Patient aged > 6 months /Both sex	Yes:	No:
2.	P. vivax mono-infection asexual parasites/ $\mu$ l Pv 250-100,000/ $\mu$ l	Yes:	No:
3.	Body weight > 5 kg	Yes:	No:
4.	Patient with fever or history of fever in the previous 24 hours	Yes:	No:
5.	Non-pregnant or breast-feeding female	Yes:	No:
6.	Ability to swallow oral medication	Yes:	No:
7.	Residents living within 5 km radius of the health centre and agree to return for all scheduled follow up visits	Yes:	
8.	Willing to give informed consent	Yes:	No:
9.	Evidence of concomitant febrile illness If "YES", indicate illness. If "NO", leave blank. 
 
☐ Pneumonia/RTI      ☐ Measles
 
☐ Otitis Media      ☐ UTI
 
☐ Gastroenteritis      Other:
 
	Yes:	No:
10.	Evidence of severe malaria / danger signs If "YES" indicate criteria. If "NO", leave blank. 
 
☐ Unarousable coma (if after convulsion, > 30 min)
 
☐ Repeated convulsions (> 2 within 24 h)
 
☐ Recent convulsions (1-2 within 24 h)
 
☐ Altered consciousness(confusion, delerium,, coma)
 
	Yes:	No:

	
 
ə Lethargy
 
ə Unable to drink or breast feed
 
ə Vomiting everything
 
ə Unable to stand/sit due to weakness
 
ə Severe anaemia (Hb < 5.0 g/dL)
 
ə Respiratory distress (laboured breathing at rest)
 
ə Jaundice (yellow colouring of eyes)
 
		
11.	Known hypersensitivity to AL/CQ/DP	Yes:	No:

If any of the responses fall into the shaded area, exclude the patient from the study

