#### ANNEX 6: Definitions of Severe Malaria

**Impaired consciousness:** A Glasgow Coma Score <11 in adults or Blantyre coma score <3 in children

**Acidosis:** A base deficit of >8 meq/l or, if unavailable, a plasma bicarbonate of <15 mM or venous plasma lactate >5mM. Severe acidosis manifests clinically as **respiratory distress** – rapid, deep and laboured breathing

**Hypoglycaemia:** Blood or plasma glucose <2.2mM (<40mg/dl)

**Severe malarial anaemia:** A haemoglobin concentration <5g/dl or a hematocrit of <15% in children <12 years of age (<7g/dl and <20%, respectively, in adults) together with parasite count of > 10,000  $\mu$ /l

**Renal impairment (acute kidney injury):** Plasma or serum creatinine >265  $\mu$ M (3 mg/dl) or blood urea >20 mM

**Jaundice:** Plasma or serum bilirubin >50  $\mu$ M (3 mg/dl) together with a parasite count >100,000  $\mu$ /l

**Pulmonary oedema:** Radiologically confirmed, or oxygen saturation <92% on room air with respiratory rate >30/min, often with chest indrawing and crepitations on auscultation

**Significant bleeding:** Including recurrent or prolonged bleeding from nose, gums, or venipuncture sites; haematemesis or melaena

**Shock:** Compensated shock is defined as capillary refill  $\geq 3$  seconds or temperature gradient on leg (mid to proximal limb), but no hypotension. Decompensated shock is defined as systolic blood pressure < 70mm Hg in children or <80 mm HG in adults with evidence of impaired perfusion (cool peripheries or prolonged capillary refill)

**Hyperparasitemia:** *P. vivax* >2%

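### Eligibility limits conflict: the enrolment step excludes Hb below 5 g/dl while the exclusion criteria bar Hb below 8 g/dl, and the day-0 rapid screen (about 1000/µl) does not match the 250/µl minimum

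*Combined protocol and SAP*

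**What the plan says.** **Haemoglobin.** The Exclusion Criteria list "Severe anemia, defined as hemoglobin (Hb) < 8 g/dl". Item 3 of Enrollment and Follow-up, the enrolment step at which Hb is measured, says that the measurement "will be carried out and those with hemoglobin <5g/dL will be excluded". On the Annex 1 Patient Screening Form the only Hb entry is severe anaemia at < 5.0 g/dL, one of the tick-boxes under item 10, "Evidence of severe malaria / danger signs". Emergency Care uses the same figure in its list of severe-malaria signs: "altered mental status, coma, convulsions, hemoglobin <5g/dl, respiratory distress". Patient Discontinuation or Protocol Violation names two enrolment violations that lead to withdrawal: "Severe malaria on day 0" and "Erroneous inclusion of a patient outside of the inclusion/exclusion criteria".

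**Parasite density.** The Inclusion Criteria require more than 250 asexual forms/µl. Item 2 of the Annex 1 form gives 250 to 100,000/µl; the Inclusion Criteria have no upper limit. Laboratory Examination describes a day-0 rapid screen whose stated purpose is to confirm the lowest density for enrolment. It sets the screen at 1 parasite per 6-8 WBC, about 1000/µl.

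**Density formula.** Laboratory Examination multiplies the count by a range, 6000-8000, and divides by about 200 leukocytes. Statistical Analysis compares mean Hb between patients at or above 10,000/µl and those below.

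**MUAC.** The malnutrition exclusion uses a mid-upper arm circumference below 100 cm in children under five. Body Weight says that the measurement is recorded to the nearest 0.2 cm.

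**The concern.** Eligibility rules should give the same answer for the same patient whichever section is open on the desk. Here a patient with Hb of 5 to < 8 g/dl passes the written enrolment step but breaches the exclusion list. Such a patient could be treated and then withdrawn, which costs evaluable patients in a study planned on 73. A patient with a density between 250 and about 1000/µl meets the inclusion criterion but falls short of the rapid screen that is meant to confirm it. If that screen decides enrolment, the patients studied have higher densities than the population the plan describes. The range in the density formula leaves one analysis grouping undefined for some counts.

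**Working it through.** **1. Haemoglobin: the sections side by side.**
- Hb < 5 g/dl: excluded by both the Exclusion Criteria and item 3.
- Hb 5 to < 8 g/dl: excluded by the Exclusion Criteria, but not by item 3 or by any Hb entry on the form.
- Hb ≥ 8 g/dl: excluded by neither.

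Item 5 then says: "After assignment, on day 0, each patient will receive the dose of treatment medication under direct observation". A patient in the middle band who is enrolled under item 3 alone is therefore dosed and afterwards meets the withdrawal rule for erroneous inclusion. The form is supporting evidence only. It is not a full checklist, since it also lacks malnutrition, QT history and contraception.

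**2. Effect on precision.** Inputs from Sample Size Determination: failure 5%, margin 5 points, 95% confidence, 20% allowance.
- The plan's figures reproduce: 1.96² × 0.05 × 0.95 / 0.05² = 72.99, so 73; 73 × 0.2 = 14.6, so 15; 73 + 15 = 88.
- Half-width = 1.96 × √(0.05 × 0.95 / n). At n = 73 it is 5.00 points.
- The share withdrawn is an assumption, because the documents give no Hb distribution. Taken from 73 evaluable (worst case):
  - 5%: 73 × 0.95 = 69.4, half-width 5.13 points
  - 10%: 73 × 0.90 = 65.7, half-width 5.27 points
  - 20%: 73 × 0.80 = 58.4, half-width 5.59 points
- Taken from the 88 enrolled, with the allowance otherwise unused: at 20%, 88 × 0.80 = 70.4, half-width 5.09 points.

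**3. Rapid screen.** Density = (parasites / WBC counted) × WBC per µl.
- Matched pairs reproduce the stated figure: 6000/6 = 1000 and 8000/8 = 1000 per µl. Against 250/µl this is 1000/250 = 4 times.
- Crossed pairs: 6000/8 = 750 and 8000/6 = 1333 per µl, or 3 and 5.3 times.
- A count that corresponds to 250/µl: 6000/250 = 24 and 8000/250 = 32, that is, 1 parasite per 24-32 WBC.

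**4. Multiplier.** 8000/6000 = 1.33, so one count can give two densities 33% apart. With 200 WBC counted, each parasite stands for 30/µl (at 6000) or 40/µl (at 8000).
- 250 parasites: 7,500 or 10,000/µl.
- 333 parasites: 9,990 or 13,320/µl.
- 334 parasites: 10,020/µl even at 6000.

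Counts of 250 to 333 therefore change side of the 10,000/µl boundary with the multiplier chosen.

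**5. MUAC.** Read literally, < 100 cm would exclude essentially every child under five, and it does not fit a measurement recorded to 0.2 cm. It is an evident threshold or unit error.

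**The case against.** The best defence on Hb is that the limits are nested. Everyone below 5 is also below 8, the exclusion list is unambiguous, and the withdrawal rule treats that list as controlling. Staff who apply both limits make no error. This stands, and it limits the harm to staff who work from item 3 and the form alone. It does not remove the conflict, because item 3 states a different rule and does not refer back to the list.

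A reader might take the point further in several ways that the documents do not support:
- *That sites would apply different limits.* Study Area and Period names one health centre. The references elsewhere to several sites or facilities name no second one. At most, staff members could differ.
- *That Annex 6 settles the Hb value, or must be reconciled with it.* It defines severe malaria, differs by age and adds a parasite-count condition. Severe malaria is excluded separately.
- *That Hb is read only after dosing.* Items 3 to 5 put the measurement before the first dose.
- *That the Hb comparisons at every visit would be altered.* Withdrawn patients would largely be absent from the later visits, so mainly the day-0 comparison is open to this.
- *That precision would suffer seriously.* Subtracting from 73 ignores the 15-patient allowance, and Kaplan-Meier censors withdrawals, so follow-up before withdrawal is kept. In fairness, that allowance is described as covering loss to follow-up and withdrawn consent.
- *That the rapid screen certainly rejects eligible patients.* It is called initial screening, no rejection rule is stated, and a definitive count follows. The mismatch is real; its effect on the sample is conditional.
- *That the multiplier disturbs the early-failure rules.* This would need it to vary between one patient's visits, which no section says. It would also need those rules to govern rather than the separate *P. vivax* failure definition in Annex 4.
- *That the formula must use one fixed constant.* Study Variables lists leukocyte count, so a patient-specific value is possible, although no section says that it is used.

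**Conclusion.** The conflict holds and should be fixed. The main defect is the 3 g/dl band (5 to < 8), which the Exclusion Criteria and the enrolment step treat differently. How many patients fall in it cannot be calculated from the documents. On an assumed 5-20% withdrawn, the half-width would be at worst 5.1-5.6 points against the planned 5.0, and no more than about 5.1 if the allowance were otherwise unused. That is a modest effect on the primary estimate.

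The density mismatch is secondary: about 4 times the stated minimum on the plan's own figures. It shifts the sample toward higher densities only if the rapid screen is used as an enrolment cut-off. The multiplier range is minor and leaves one grouping undefined for counts of 250-333 per 200 WBC. The MUAC limit is clerical. No view is taken on which Hb or density limit is right.

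**What to change.** 1. Reconcile the Exclusion Criteria and Enrollment and Follow-up item 3 to one Hb exclusion value, and put that value on the Annex 1 form as its own item, apart from the danger-sign list.
2. Reconcile the Inclusion Criteria, the rapid-screen rule in Laboratory Examination and item 2 of the Annex 1 form so that the screening count and the minimum agree. For reference, 250/µl is 1 parasite per 24-32 WBC. State in both the Inclusion Criteria and the form whether the 100,000/µl upper limit applies.
3. State which value the density formula uses, either one fixed constant or the patient's measured leukocyte count, and apply it consistently.
4. Correct the MUAC threshold or unit.

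The cost is a few lines of wording and one added form item. Hb is already measured on day 0, so no new test is needed. If the rapid screen is aligned to 250/µl, low-density slides will take slightly longer to read.
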